1.3 Definition of the safety variables

Hypoglycaemia is the main adverse event and safety issue in the study. Previous studies suggest that employing strict glycaemic control in a population of Intensive Care patients will result in between 5 and 42 episodes of severe hypoglycemia for every 100 patients recruited to the lower range group and less than 5 episodes of severe hypoglycemia for every 100 patients recruited to the higher range group. The incidence of severe hypoglycemia and clinical consequences of severe hypoglycemia will be compared across treatment arms.

1. Number of patients suffering severe hypoglycemia (documented blood glucose concentration of 2.2mmol/L or less [40mg/dL or less] at any time in the ICU within 90-days of randomization) and number of episodes of severe hypoglycaemia occurring in the ICU within 90-days of randomization.
2. Incidence of clinical consequence of severe hypoglycemia
 - I. Neurological
 - II. Cardiovascular
 - III. Other

1.4 Analysis principles

1. All analyses will be conducted on an intention-to-treat basis.
2. All tests are two-sided and the nominal level of α will be 5%.
3. All statistical analyses will be unadjusted except where indicated.
4. Subgroup analyses will be carried out irrespective of whether there is a significant effect of treatment on the primary outcome.
5. We will not impute missing values unless specified otherwise. Where the number of missing observations is substantial, we will report the number of observations used in the analysis. Last observations will not be carried forward for continuous outcomes, e.g. the SOFA scores.
6. P-values will not be adjusted for multiplicity. However the outcomes are clearly categorized by degree of importance (primary to tertiary) and a limited number of subgroup analyses are pre-specified.

2. DESIGN ISSUES

2.1 Data collection Follow-up

The different stages of data collection and follow-up can be summarised in the diagram below:

Form No.	Period of study	Data collection
	Randomization	Patient demographics and inclusion/exclusion criteria
1	Baseline	Source and date of admission to ICU, ICU admission diagnosis, sub-group categorize operative or non-operative admission and presence or absence of 'severe sepsis', 'trauma', traumatic brain injury and patients with Type I or Type II diabetes, Acute Physiology and Chronic Health Evaluation (APACHE) II score, SOFA scores (CVS, respiratory, hepatic, renal, haematologic), use of renal replacement therapy, use of mechanical ventilation, blood glucose concentration (last measurement before randomization), height and weight, prior treatment with insulin and corticosteroids.
2	Hourly, Days 1 - 90	Post-randomization blood glucose concentration whilst in ICU for maximum of 90 days. We will report the overall mean and standard deviation (SD) of daily early morning (first measurement after 08.00) blood glucose and daily time-weighted mean [#] blood glucose concentration measured from randomization to the earlier of ICU discharge or 90 days, the mean and SD early morning (first measurement after 08.00) and time-weighted [#] average blood glucose concentration measured from randomization to the time the patient's blood glucose is no longer managed according to the treatment algorithm (indicating cessation of study treatment). Results will be displayed as a plot of mean over time by treatment arm. They will be truncated at a relevant number of days. e.g. 14 days.
3	Daily, Days 1 - 90	Whilst in ICU: Daily SOFA scores (CVS, respiratory, hepatic, renal, haematologic), treatment with renal replacement therapy or mechanical ventilation, type (enteral versus parenteral) and volume of nutrition administered (total non-protein calories, protein, carbohydrate, lipid will be calculated from type and volume of enteral and parenteral nutrition administered), all iv glucose administered, all positive blood culture results that are clinically significant by predefined criteria. Total amount of insulin administered. Total amount of corticosteroids given (calculated as hydrocortisone equivalent). Number of patients transfused RBCs and volume of red blood cells (RBCs) transfused per randomised patient. Number of patients with treatment limitation order timing of and reason for treatment limitation.

4	28 Day Summary	Vital status (alive or dead) at day 28. Place, date and cause of death, date of discharge from ICU, date of discharge from hospital, number of days in ICU, type of consent obtained.
5	90 Day Summary	Vital status at day 90, length of stay in ICU, length of stay in hospital, place, date and cause of death
6	Serious Adverse Event of Hypoglycaemia	Description, date and time, cause and resolution of any serious adverse events whether or not study-related, severe hypoglycaemia (no. of episodes < 2.2 mmol/L or 40mg/dL, signs & symptoms, treatment given)
7	Extended Glasgow Outcome Score	Outcome score at 6 month and 2 year follow up for patients with TBI (history of trauma, cranial CT scan consistent with traumatic brain injury, and last unседated pre-randomization GCS <14)

A daily time-weighted blood glucose (weighting based on time difference between two consecutive measurements applied to the average of two consecutive measurements) is to be computed for Item 2. Any consecutive BGA measurements within a study day are treated as continuous process. In the case where BGA measurements are taken over more than a study day, they are treated as the start of new treatment and discontinuous from the first. Unweighted blood glucose calculations will also be provided for comparison.

Due to local legal considerations, patients or their legal surrogate may have an absolute right to request that their data be removed from the study database; as a result there are potentially two data sets: the randomized patients and the randomized patients where data is available. The latter is obtained after *deleting the data for randomized patients who withheld or withdrew their consent and did not allow their data to be submitted or maintained* in the database – see section II 6 for details. Only the latter dataset can be used in the analysis.

2.2 Study design

The NICE-SUGAR study is a multi-centre, open label, randomized concealed, controlled trial.

2.3 Treatment allocation

Eligible patients will be randomized to one of the two blood glucose targets using minimization. Two strata will be considered: the type of critical illness (post-operative versus non-operative) and geographic region (Australia and New Zealand versus North America). Centralized randomization will be achieved via a password-protected web-based program.

2.4 Power

We plan to enrol 6100 patients providing 90% power to detect an absolute decrease in mortality of 3.8% from a baseline of 30% (two-sided alpha <0.05). The study is powered to detect a relative risk reduction of 12.7%, which is 37% of the treatment effect documented in Van den Berghe's first study,¹ this difference is clinically important and if detected would likely lead to widespread change in the practice of glycemetic control in ICU's in Australia, New Zealand, North America and beyond.

2.5 Interim analyses

An independent Data and Safety Monitoring Board (DSMB) chaired by [name] Peto in Oxford, England, will review unblinded data on patient characteristics, treatment compliance and study outcomes at two interim analyses (availability of primary outcome for 1500 and 4000 patients) and at the final analysis. Recruitment will be reviewed at regular intervals during the trial, to be determined by the DSMB which will generate terms of reference. The DSMB will be charged with informing the Study Management and Executive Committees if at any time there emerges: 1) Evidence beyond reasonable doubt of a difference between randomized groups in all-cause mortality, or 2) Evidence likely to change the practice of many clinicians already familiar with the available evidence about the trial interventions.

2.6 Dates and consent-related issues

Dates will be queried so that no missing values remain. Due to the specific nature of the study informed prior consent is not always possible and a patient or their legal surrogate may be asked for a delayed consent. Two important situations can lead to the cessation of study treatment: 1) a patient or next of kin or legal surrogate may withdraw consent or 2) they may refuse *continuation* of study treatment when delayed consent is sought (as opposed to withdrawing an existing consent). In both cases the study treatment will cease and the patient will receive glycaemic control as prescribed by their treating clinicians. In this situation specific consent is sought to continue study follow-up procedures and to use study data. If consent for use of data is withheld, that patient's data will be removed from the analysis except for data related to consent. Censoring dates will only occur in case of 'real' loss to follow-up, i.e. discharged patients with no information beyond some point in time. In that case the date of censoring will be the last day of contact or the date of hospital discharge if no other information is available.

[figure not shown]
2.7 Permanent discontinuations

The data of patients who withdraw or withhold consent to continued study treatment but consent to the use of their data will remain in the analysed data set and will be analyzed on an intent-to-treat basis. Vital status at 28 or 90 days will not be imputed if this information is missing.

3. STATISTICAL ANALYSIS

3.1 Trial profile

Flow of patients through the study will be displayed in a “CONSORT” diagram. We will report number of screened patients who met study inclusion criteria and number included, reasons for exclusion of non-included patients and information as below:

Loss to follow up = any patient for whom the primary outcome was not available;
 analysed = all patients for whom the primary outcome was available.

3.2 Characteristics of patients and baseline comparisons

Description of the following baseline characteristics will be presented by treatment group. Discrete variables will be summarised by frequencies and percentages. Percentages will be calculated according to the number of patients for whom data are available. Where values are missing, the denominator (which will be less than the number of patients assigned to the treatment group) will be stated in either the body or a footnote in the corresponding summary table. In some instances frequencies and percentage of patients in the category will be reported as indicated in the list below.

Continuous variables will be summarised by use of standard measures of central tendency and dispersion, either mean and SD for variables identified with #, or median and interquartile range (IQR) for symbol †. Medians (IQR) will be added as summary measures.

Baseline measures for all patients

1. Sex
2. Age #
3. Weight #
4. Height #
5. Calculated body mass index #
6. Geographic region (Australia and New Zealand vs. North America)
7. Source of admission to ICU (emergency department, hospital floor, another ICU, another hospital, operating room (OR) following emergency surgery, OR following elective surgery, readmission to the same ICU during same hospitalization)
8. Time from ICU admission to randomization
9. Operative versus non-operative
10. Operative admission diagnosis (number and % in categories a-k)
 - a. Cardiovascular
 - b. Respiratory
 - c. GIT
 - d. Neurological
 - e. Trauma without traumatic brain injury
 - f. Traumatic brain injury +/- multiple trauma
 - g. Burns
 - h. Renal
 - i. Gynecology
 - j. Other orthopedic
 - k. Other surgical
11. Non-operative admission diagnosis (number and % in categories a-l)
 - a. Cardiovascular
 - b. Respiratory
 - c. GIT
 - d. Neurological
 - e. Sepsis
 - f. Trauma without traumatic brain injury
 - g. Traumatic brain injury +/- multiple trauma
 - h. Metabolic
 - i. Hematological
 - j. Burns
 - k. Renal
 - l. Other medical
12. Severe sepsis at baseline
13. Trauma with or without brain injury at baseline
14. Traumatic brain injury at baseline

15. APACHE II score #
16. SOFA score
 - a. Cardiovascular component
 - b. Respiratory component
 - c. Renal component
 - d. Hepatic component
 - e. Haematologic component
17. Last blood glucose concentration before randomization #
18. Prior history of diabetes mellitus
 - a. Type I
 - b. Type II
19. Patient normally treated with insulin (n / %)
20. Renal replacement therapy at baseline (n / %)
21. Mechanical ventilation at baseline (n / %)
22. Treatment with corticosteroids at baseline (n / %)

Additional baseline measures for patients with trauma

Injury severity score (1998 version)[†]

Additional baseline measures for patients with traumatic brain injury

1. Glasgow coma score at baseline[†]
 - a. Eye component[†]
 - b. Verbal component[†]
 - c. Motor component[†]
2. Marshall score for CT brain
(n and % of patients in each of the 5 categories)
3. Incidence of hypotension (SBP<90mmHg or MAP<65mmHg) prior to randomization
4. Intracranial pressure (ICP) monitor at baseline (n / %)
5. ICP at baseline (when measured) #

3.3 Process measures and concomitant treatments

Categorical or continuous variables and times to-event will be summarised as described in 1. When indicated, frequencies and percentages of patients per category will also be given. Again the same coding using # for mean (SD) and † for median and IQR will be used to indicate the presentation of measures of central tendency and dispersion. Standard Chi-square tests will be performed to compare frequencies and t-test or Wilcoxon rank sum test used for continuous data. In case of rare events (expected number per cell lower than 1) the Fisher test will be used.

Process Measures

1. Time on study treatment
2. Time from cessation of study treatment to (last) discharge from the ICU
3. Number (%) patients treated with insulin in the ICU within 90 days of randomization
4. Daily insulin dose (IU/days on study treatment) #
5. Mean morning (first measurement after 08.00) blood glucose concentration by group#
 - a. Averaged over time from randomization to time of ICU discharge #
 - b. Averaged over time from randomization to time study treatment stopped (if study treatment is stopped and then restarted, all episodes on study treatment will be used to calculate the average) #
6. Mean time-weighted blood glucose concentration by group
 - a. Averaged over time from randomization to time of ICU discharge #

- b. Averaged over time from randomization to time study treatment stopped (if study treatment is stopped and then restarted, all episodes on study treatment will be used to calculate the average) #

Concomitant treatments

7. Non-protein calories administered in the ICU (by day, up to day 14) #
 - a. Non-protein calories by all routes (by day, up to day 14) #
 - b. Non-protein calories by enteral route (by day, up to day 14) #
 - c. Non-protein calories by parenteral route (by day, up to day 14) #
 - d. Non-protein calories as intravenous glucose (by day, up to day 14) #

In addition, bar graphs displaying means (SD) of total non-protein calories and non-protein calories by the enteral route per treatment group by the day in ICU will also be produced (detailed in Section 5). In the event that the number of patients remaining in the ICU becomes too small, the means will be truncated prior to 14 days. Conversely the maximum of 14 days will be extended if considered relevant by the study statistician.

8. Patients treated with corticosteroids at any time in the ICU
Daily dose of corticosteroid as hydrocortisone equivalent (by day, up to day 14) #

Limitation of treatment

9. Patients for whom there was limitation of treatment.
10. Patients for whom treatment limited or withheld
 - a. Patients for whom treatment limited as terminal event
 - b. Patients for whom maximal treatment was not indicated
11. Time from randomization to first treatment limitation order (overall and for limitations indicated in 10 a. and 10 b.)

Treatment limitation refers to a) withdrawing a treatment that might otherwise prolong life as it is no longer considered appropriate for that individual, i.e. stopping of a previously provided treatment or b) withholding treatment that might otherwise prolong life as it is not considered appropriate for that individual, i.e. not commencing a treatment. Each of these will have been authorized by a treating clinician independent of the study and documented in the medical record. The specific treatments limited or withdrawn will not be reported.

Consent and Permanent discontinuation of study treatment

12. Consent (n and % in each category a-f)
 - a. Prior informed consent from patient
 - b. Prior informed consent from a legal surrogate
 - c. Delayed informed consent from patient
 - d. Delayed informed consent from a legal surrogate
 - e. Consent from other legal body before or after patient's death
 - f. No consent obtained – data withdrawn

13. Patients for whom study treatment permanently discontinued (n and % in each category a-f)
 - a. Patients for whom informed consent withdrawn
 - b. Patients for whom delayed informed consent withheld
 - c. Study treatment discontinued by treating clinician (not due to SAE or palliative care)
 - d. Study treatment discontinued due to SAE
 - e. Study treatment discontinued as focus of treatment changed to palliative care
 - f. Study treatment discontinued for other reason

3.4 Description of analyses

3.4.1 Primary outcome

A standard Chi-square test will be used as the primary test of statistical significance of the effect of treatment allocation on 90-day all cause mortality. Frequencies and percentages per arm, an odds-ratio measuring the treatment effect and its 95% confidence interval (CI) will also be reported. We will also perform an adjusted analysis for sensitivity purposes. It will be based on a multivariate logistic regression analysis adjusted for strata used in minimization, i.e. post-operative versus non-operative patients and region and the following predictors: age, ICU admission source, APACHE II score and mechanical ventilation at baseline. In the event the DSMB considers early stopping of the trial, the results of this analysis will be reported to the management committee and DSMB before a final decision to suspend recruitment is made. A sensitivity analysis will be performed if more than 5% of the 90 day mortality data are missing.

Specific analysis for patients with traumatic brain injury (TBI)

In addition, a specific analysis will be carried out for patients with TBI. In that case the primary outcome will be the GOSE at 2 years. A Wilcoxon rank-sum test adjusted for ties will be used to assess the effect of treatment on the GOSE condensed to four categories listed below:

- 1 - dead or vegetative state
- 2 - severe disability
- 3 - moderate disability
- 4 - good recovery

Frequencies and percentages will be presented by categories. We will also perform an adjusted analysis for sensitivity purposes. It will be based on an ordinal regression analysis, ³ adjusted for the following known predictors: age, last unsedated pre-randomization Glasgow coma score (GCS), presence of pre-randomization hypotension (defined as a documented systolic arterial blood pressure of less than 90mmHg or documented mean arterial blood pressure of less than 65mmHg) and presence of traumatic subarachnoid hemorrhage (tSAH) on a pre-randomization computerized tomographic (CT) brain scan. If the proportional-odds assumption needed for ordinal regression to be valid is grossly violated, alternative models will be investigated. The list of predictors used for adjustment can be shortened in case of instability – for example, if there are too many zero values, or if missing values on a particular covariate substantially reduce the size of the working sample size. In the extreme case of small numbers categories in 1-4 will also be collapsed, the decision being made on blinded data by the study management committee.

The vital status at 90 days of TBI patients will also be displayed as number and percentage of deaths per treatment arm. A comparison of these proportions will be based on a Chi-square test with odds ratio and 95% CI.

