1.1.5 Objectives

The primary aim of the study is to compare the effects of the two regimens targeting different blood glucose concentrations on 90-day all-cause mortality in Intensive Care patients who are predicted on admission to the ICU to be treated in the ICU on three consecutive calendar days. The null hypothesis is that there is no difference in the relative risk of death between patients assigned to a target glucose concentration of 4.5 - 6.0 mmol/L and those assigned to target a glucose concentration of less than 10.0 mmol/L with insulin being infused if blood glucose exceeds 10.0 mmol/L, and adjusted when needed to maintain blood glucose of 8.0 – 10.0 mmol/L.

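### The primary test of 90-day mortality leaves out covariates that the SAP already models, and only the odds ratio has a planned confidence interval: room for improvement, not an error

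*SAP*

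**What the plan says.** Section 2.3 allocates by minimisation: "Two strata will be considered: the type of critical illness (post-operative versus non-operative) and geographic region". Section 3.4.1 then fixes the primary analysis: "A standard Chi-square test will be used as the primary test of statistical significance", and "Frequencies and percentages per arm, an odds-ratio measuring the treatment effect and its 95% confidence interval (CI) will also be reported".

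The same paragraph sets out a logistic regression with both minimisation factors plus age, source of ICU admission, APACHE II score and mechanical ventilation at baseline. It is ranked as a sensitivity analysis. Section 1.4 makes unadjusted analysis the default and rules out imputation unless it is specified.

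On the scale of the effect, section 1.1.5 says "The null hypothesis is that there is no difference in the relative risk of death". Section 2.4 says "We plan to enrol 6100 patients providing 90% power to detect an absolute decrease in mortality of 3.8% from a baseline of 30" per cent ("two-sided alpha <0.05") and restates this effect as a relative risk reduction of 12.7%.

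**The concern.** There are two separate issues.

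**Efficiency.** Minimisation forces balance on two factors, but the standard error of a crude chi-square takes no credit for it. Nor does the crude test use age, APACHE II, admission source or ventilation, which are collected at baseline and which the SAP itself names as predictors. The analysis that uses this information is already written but ranked second. What is at stake is precision that would need no extra patients or data.

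**Reporting.** The trial is justified on relative risk and on an absolute difference, yet the text plans an interval for neither. With mortality near 30%, an odds ratio is clearly further from 1 than the relative risk, so it does not express the effect in the terms in which the trial was justified.

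**Working it through.** **Inputs.** From section 2.4: N = 6100, 30.0% versus 26.2% mortality, two-sided 0.05. From section 3.5: final critical value 1.975. Allocation 1:1 is assumed, since section 2.3 gives no ratio. The prognostic strength of the covariates and the mortality by operative status are also assumed.

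**1. The plan's own power.** With n = 3050 per arm and mean risk 0.281:

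z = [0.038 × √3050 − 1.96 × √(2 × 0.281 × 0.719)] / √(0.30 × 0.70 + 0.262 × 0.738) = (2.0986 − 1.2459) / 0.6351 = 1.343, so power = 91.0%.

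At 1.975 power is 90.8%. For 90% power N is 5878, or 5982 with continuity correction. The stated 90% is reproduced, and 3.8/30 = 12.7% agrees.

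**2. What minimisation does to the chi-square.** Take one binary factor, perfectly balanced, with overall mortality 30%. Let v be the ratio of within-stratum to total variance. The crude test then has true alpha 2 × [1 − Φ(1.96/√v)].

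- Operative/non-operative mortality 26%/33%: v = 0.994, alpha 0.049. Power is 91.1% crude and 91.2% stratified.
- 15%/42%: v = 0.914, alpha 0.040. Power is 92.0% crude and 93.2% stratified.

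The crude test errs on the safe side, and adjusting for such a factor alone adds about 0.1 to 1.3 points.

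**3. What the predictors add.** Trials of 6100 patients were simulated with marginal risks of 30% and 26.2% and one normally distributed prognostic score, 2500 runs per row (Monte Carlo error about 0.6 points).

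| c-statistic (assumed) | Unadjusted power | Adjusted power | Conditional odds ratio |
|---|---|---|---|
| 0.63 | 90.7% | 92.0% | 0.821 |
| 0.70 | 90.3% | 93.6% | 0.810 |
| 0.75 | 89.1% | 94.6% | 0.801 |
| 0.79 | 91.2% | 96.0% | 0.785 |

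The marginal risks are the same in every row, so the unadjusted column should be 91.0% throughout and its spread is simulation noise. Read against 91.0%, the gain is about 1 to 5 points.

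As a cross-check, a second simulation found that the score explained 0.099, 0.157 and 0.228 of the outcome variance at c-statistics of 0.69, 0.74 and 0.79. Information then grows by 1/(1 − R²) = 1.11, 1.19 and 1.30. The crude standardised effect is 0.038/√(2 × 0.281 × 0.719/3050) = 3.301. Φ(3.301 × √[1/(1 − R²)] − 1.96) gives 93.6%, 94.9% and 96.4%, against simulated values of 93.6%, 94.7% and 96.1%.

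**4. The three scales at the design rates** (95% intervals, multiplier 1.96):

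- Risk difference: −3.8 points (−6.1 to −1.5).
- Relative risk: 0.262/0.30 = 0.873 (0.806 to 0.947), a 12.7% reduction.
- Odds ratio: (0.262/0.738)/(0.30/0.70) = 0.828 (0.741 to 0.926), a 17.2% reduction in odds.

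**The case against.** The strongest case is that the SAP makes a declared and valid choice. Section 1.4 sets the unadjusted rule, the sample size was computed for the unadjusted comparison, and the adjusted model is fully specified. That model also appears to be the analysis that must go to the management committee and DSMB before any early-stopping decision. A chi-square uses every patient with a known outcome and needs neither a model nor baseline imputation. The power gain rests on assumed prognostic strength, and the simulated model is correctly specified, which is a favourable case. All of this stands. It bears on how much weight the point deserves, but gives no reason to leave the gain unused.

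The documents do not support several stronger readings that a reader might infer:

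- *The test is invalid under minimisation.* Step 2 shows the reverse: it is slightly conservative.
- *The trial is underpowered.* The planned power is met.
- *The plan ignores the minimisation factors.* Only the primary test does.
- *Hypothesis and test conflict.* A relative risk of 1, an odds ratio of 1 and a risk difference of 0 are the same null hypothesis.
- *The odds ratio is the only result reported.* Deaths and percentages per arm are also planned, so the other two estimates can be derived by any reader.

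Section 3.6 places the table formats in an attached spreadsheet that is not among the documents at hand. It may contain further intervals; the text of section 3.4.1 does not plan them.

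**Conclusion.** The point holds as an improvement in efficiency and reporting. Promoting the adjusted model would raise power from about 91% to about 92-96%, on the assumption that its covariates reach a c-statistic of 0.63 to 0.79. Most of the gain comes from age, APACHE II, admission source and ventilation; the minimisation factors contribute little. If the true prognostic strength is at or below the lower end, the gain is about one point or less.

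The reporting part needs no assumption beyond the design rates. The text plans no interval on either scale used to justify the trial, and at those rates a 12.7% reduction in risk corresponds to a 17.2% reduction in odds. This would mislead only a reader who took the odds ratio for a relative risk, which the SAP itself never does.

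**What to change.** Amend section 3.4.1 before unblinding:

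1. Make the logistic model already specified the primary test, and keep the chi-square as the supporting analysis shown beside it.
2. Specify simple imputation of missing baseline covariates, so that no patient with a known outcome is dropped. Section 1.4 permits imputation where it is specified.
3. Report the risk difference and relative risk, standardised from the model, with confidence intervals beside the odds ratio. State the variance method, and use the multiplier that section 3.5 prescribes for the final interval.

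Item 3 matters more once the model is primary. The adjusted odds ratio is conditional on the covariates and lies further from 1 than the crude one (0.821 to 0.785 in the table, against 0.828), so the two should not be presented as the same quantity.

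The cost is SAP wording and some programming. The real downside is that the headline test becomes model-based and needs a standardisation step. If the chi-square stays primary, the SAP should say why, and the relative risk and risk difference should still be given intervals.
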